1. BACKGROUND AND RATIONALE

1.1 General Introduction

Diabetic foot ulcers (DFUs) are a common problem with clinically serious sequelae. It has been reported that annually, about 1% to 4% of those with diabetes, which is believed that more than 23 million people in the United States have, develop a foot ulcer; 10% to 15% of those with diabetes will have at least one foot ulcer during their lifetime. DFUs place patients at the risk of lower extremity amputations (LEAs), which is an extremely complicated. In the U.S., around 80,000 LEAs annually are conducted on diabetics.^{1,2} In 2005, the overall rate of hospital discharge for new LEA was about 4.3 per 1,000 diabetic people.³ As a result, DFUs are widely acknowledged a source of major distress and morbidity for diabetic patient and also an enormous drain on health-care resources. It then becomes an important issue to have an effective treatment to alleviate the ulcer worsening and even to achieve complete ulcer closure for DFU patients.

Wound healing process is a complex series of events that comprised of inflammatory, proliferative (including granulation, contraction, epithelialization) and remodeling phases. Excessive inflammatory stimuli may be deleterious and result in adverse consequence to wound healing. Antioxidants, on the other hand, significantly limit the delayed sequelae of tissue damage and stimulate wound healing process. As a result, many substances that intend to enhance the wound healing emphasis on their anti-inflammatory and antioxidant effects.^{4,5}

[REDACTED]

[REDACTED]

[REDACTED]

[REDACTED]

[REDACTED]

[Redacted text block]

[Redacted text line]

[Redacted text line]

[Redacted text line]

[Redacted text line]

[Redacted text block]

[Redacted text line]

[Redacted text block]

[Redacted text line]

[Redacted text block]

[Redacted text line]

[Redacted text block]

[Redacted text line]

[Redacted text block]

[Redacted text block]

1.2 Rationale and Justification for the Study

1.2.1 Rationale for the Study Purpose

[Redacted text block]

1.2.2 Rationale for Doses Selected

[Redacted text block]

1.2.3 Rationale for Study Population

[Redacted text block]

1.2.4 Rationale for Study Design

[Redacted text block]

2. OBJECTIVES AND ENDPOINTS

2.1 Objectives

2.1.1 Primary Objectives

The primary objective of this study is to evaluate the efficacy of CSTC1 in patient with diabetic foot ulcers.

2.1.2 Secondary Objectives

The secondary objective of this study is to evaluate the safety of CSTC1 in patient with diabetic foot ulcers.

The study purpose is for registration. The study results may be used for developing new drug application dossier.

2.2 Endpoints

2.2.1 Primary endpoints

Incidence of complete ulcer closure during up to 12 weeks of treatment period

Complete ulcer closure is defined as 100% skin re-epithelialization without drainage or dressing requirements confirmed at two consecutive study visits 2 weeks apart.

2.2.2 Secondary efficacy endpoints

1. The ulcer closure time

Defined as the time to complete ulcer closure

2. The complete ulcer closure rate

The proportion of subjects with complete ulcer closure at each post-treatment visit

3. Percentage change in ulcer size for each post-treatment visit

Calculated as (Ulcer size at post treatment visit - Ulcer size at baseline)/(Ulcer size at baseline)

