3. Net change from baseline in laboratory test results (include hemoglobin, hematocrit, RBC, platelet, WBC with differential counts, HbA1c, fasting glucose, AST, ALT, creatinine and BUN)
4. Net change from baseline in vital signs

Statistical Analysis Analysis population

Three data sets will be introduced for statistical analysis.

Intent-to-treat (ITT) population:

- All randomized subjects who have received at least one dose study medication.

Per-protocol (PP) population:

- A subset of ITT population
- Fulfill all inclusion and exclusion criteria
- Dosed with at least 8 weeks study drug or with early confirmed complete ulcer closure AND with at least 70% treatment compliance
- Did not receive any prohibited treatment during treatment period
- With any post-treatment assessment relevant to efficacy endpoint up to end of dosing period

Efficacy endpoints will be analyzed on ITT and PP population.

Demographics, baseline characteristics, and safety endpoints will be analyzed on ITT population. Conclusion of efficacy will be made according to the result of ITT population analysis.

Analysis

Demographics and baseline characteristics will be summarized for each group by using descriptive statistics.

The efficacy endpoints will compare the CSTC1 group with vehicle group. Incidence of ulcer closure and ulcer closure rate at endpoint will be analyzed with Cochran-Mantel-Haenszel test (CMH test). Ulcer closure time will be estimated by using Kaplan-Meier methods and compared between groups by using log-rank test. Percentage change in ulcer size will be analyzed by using Analysis of variance (ANOVA) model with treatment group and center as factors. Further efficacy analyses with ankle brachial index (ABI) (<0.7 or not) as stratification may be performed if necessary.

For safety analyses, adverse events will be reported by treatment groups and by physiological systems as appropriate. Incidence of adverse events between treatments will be analyzed by CMH test. Changes in physical examinations will be displayed for each individual system. Net changes from pre-treatment laboratory test results and vital signs will be analyzed by descriptive statistics.

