Additionally, descriptive statistics will be provided for all of the endpoints. Frequency table will be provided for categorical data, while mean, standard deviation, maximum, minimum, median, inter-quartile range (IQR), and 95% two-sided confidence interval will be calculated for continuous measurements. In addition, endpoints of time to event will be presented by using the life table and Kaplan-Meier plot. The Kaplan-Meier estimates will also be provided for these time-to-event endpoints.

All treatment group comparisons will be conducted with significance level of 0.05.

SCHEDULE OF ASSESSMENTS

	Screening ¹	Initial ² Phase	Randomization ³ (Baseline)	Dosing/Observation								Follow-up			
	1	2	3	4	5	6	7	8	9	10	11 ¹¹	12	13	14	15
Week relative to Baseline visit	-3~-2	-2~0	0	1	2	3	4	6	8	10	12	14	16	20	24
Visit Window (days)	NA	±4	NA	±4	±4	±4	±4	±4	±4	±4	±4	±4	±4	±4	±4
Informed consent signed and given	X														
Screening number assignment	X														
Randomization			X												
Demographic data & medical history	X														
Inclusion and exclusion criteria	X		X												
Pregnancy test for applicable subjects	X										X				
Ulcer Evaluation ⁴	X		X	X	X	X	X	X	X	X	X	X	X	X	X
Vital signs	X		X	X	X	X	X	X	X	X	X	X	X	X	X
Physical examinations	X		X	X	X	X	X	X	X	X	X	X	X	X	X
Ankle Brachial Index ⁵	X														
Laboratory test: hemoglobin, hematocrit, RBC, platelet, WBC with differential counts, HbA1c, fasting glucose, AST, ALT, creatinine and BUN, albumin	X ⁶		X ⁷								X ⁸				
Record concomitant medication(s)	X	X	X	X	X	X	X	X	X	X	X	X	X	X	X
Standard of Care		X	X	X	X	X	X	X	X	X	X				
Record adverse events (AE) ⁹	X	X	X	X	X	X	X	X	X	X	X	X	X	X	X
Dispense trial medication			X	X	X	X	X	X	X	X					
Returned medication count				X	X	X	X	X	X	X	X				
Diary Dispensing			X												
Diary Return				X	X	X	X	X	X	X	X				
Complete exit form													X		X
Dismiss subject ¹⁰													X		X

Footnote:

- 1: Could be on the same day as the first day of Initial Phase or randomization visit if subject's Initial Phase can be waived
- 2: Can be waived if subject's diabetic foot ulcer(s) has been treated for at least 2 weeks, and is still eligible to enter this study
- 3: Could be on the same day as the last day of Initial Phase
- 4,10: Subjects with confirmed complete ulcer closure up will be arranged for ulcer evaluation for follow-up period; Subjects not with complete ulcer closure will take 4 weeks of safety evaluation

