- 5: The two blood pressures for calculating ABI, ankle and brachium, should be measured on the same side (left to left, right to right) and should be on the same side of target diabetic foot ulcer. However, the blood pressures of brachium may not be available for some patients. For such case, investigator is suggested trying to measure pressure of brachium of another side.
- 6: Test results within 14 days before Screening visit are acceptable; HbA1c test result within 28 days can be accepted. Albumin test will only be done at Screening and Randomization visits
- 7: Test results within 28 days before Randomization visit are acceptable
- 8: Test results within time window are allowed
- 9: AE should be recorded since informed consent is signed
- 11: For subject who has been confirmed complete closure before week-12 visit should be arranged for visit 11 assessment.

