4. STUDY DESIGN

This study is designed as a randomized, double-blind, vehicle-controlled, multiple center and parallel trial to evaluate the efficacy and safety of CSTC1 in patients with diabetic foot ulcer.

The potential subjects with diabetic foot ulcer at Screening visit will be arranged to enter an initial phase for 2 weeks in which subjects receive only standard of care, unless subject has receive any other regular therapy for at least 2 weeks. Subjects whose study ulcer size decreases by at least 30% during this initial standard-of-care phase or previous regular therapy period will be excluded from the study at investigator's discretion. The remaining eligible subjects will be randomly assigned to receive either one of topical application of CSTC1 dose or CSTC1 matched vehicle, 2 times daily.

The treatment duration for each subject is 12 weeks or up to confirmed complete ulcer closure, whichever comes first. That is, subjects will receive treatment for at most 12 weeks, which consists of 8 visits located at weeks 1, 2, 3, 4, 6, 8, 10, and 12. Subjects confirmed complete ulcer closure during treatment period will be arranged for a 12 week post-treatment follow-up. Subjects failed to achieve complete ulcer closure at week-12 visit will be arranged for 4 weeks of safety follow-up. Subjects happening to attain complete ulcer closure at week-12 visit will not receive further treatment but needs to be confirmed at week-14 visit. If confirmation of complete ulcer closure is reached at week-14 visit, the subject will continue the post-treatment follow-up visit until week-24 visit. Otherwise, the subject will be arranged for safety follow-up until week-16 visit.

After the treatment period, the post-treatment follow-up period for subjects confirmed complete ulcer closure will consist of 4 visits at weeks 2, 4, 8, 12 after confirmation of complete ulcer closure. The safety follow-up period for subjects failed to achieve complete ulcer closure at week-12 visit will consist of 2 visits at weeks 14 and 16.

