10.2 Statistical and Analytical Plans

10.2.1 Analysis Population

Three data sets will be introduced for statistical analysis.

Intent-to-treat (ITT) population:

- All randomized subjects who have received at least one dose study medication.

Per-protocol (PP) population:

- A subset of ITT population
- Fulfill all inclusion and exclusion criteria
- Dosed with at least 8 weeks study drug or with early confirmed complete ulcer closure AND with at least 70% treatment compliance
- Did not receive any prohibited treatment during treatment period
- With any post-treatment assessment relevant to efficacy endpoint up to end of dosing period

Efficacy endpoints will be analyzed on ITT and PP population. Demographics, baseline characteristics, and safety endpoints will be analyzed on ITT population. The conclusion of efficacy will be made according to the results of ITT population analysis.

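### Ulcer size change is defined at every post-treatment visit and compared by ANOVA, but only confirmed closers can be due after week 16, and no visible text says which visits are tested

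*Combined protocol and SAP*

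**What the plan says.** - **Endpoint.** Section 2.2.2 and the Protocol Summary define the third secondary efficacy endpoint as "Percentage change in ulcer size for each post-treatment visit". Neither gives a last visit. The closure rate is defined per visit too: "The proportion of subjects with complete ulcer closure at each post-treatment visit".
- **Test.** The Protocol Summary (Statistical Analysis) states: "Percentage change in ulcer size will be analyzed by using Analysis of variance (ANOVA) model with treatment group and center as factors". It names no visit. Two sentences earlier, the closure-rate test is tied to the endpoint. The Summary also says that "descriptive statistics will be provided for all of the endpoints" and sets 0.05 for all group comparisons.
- **Use of the term.** The per-protocol definition in section 10.2.1 requires: "With any post-treatment assessment relevant to efficacy endpoint up to end of dosing period". There, post-treatment covers visits during dosing, and a stopping point is written in.
- **Non-closers.** The Schedule of Assessments marks ulcer evaluation through week 24, but its footnote 4,10 says: "Subjects not with complete ulcer closure will take 4 weeks of safety evaluation". Sections 4 and 7.6 end these subjects' visits at week 16.
- **Closers.** For closure first seen at week 12 and confirmed at week 14, section 4 says "the subject will continue the post-treatment follow-up visit until week-24 visit". In general, sections 4 and 7.6 count follow-up from confirmation (section 4: 2, 4, 8 and 12 weeks). The Schedule (weeks 14, 16, 20, 24) and section 7.5 (weeks 14, 16, 20) fix the calendar weeks.
- **Week 12.** Schedule footnote 11 keeps this visit for early closers: "For subject who has been confirmed complete closure before week-12 visit should be arranged for visit 11 assessment".

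The secondary-endpoint analysis text in section 10.2.2 is redacted.

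**The concern.** The endpoint definition reaches weeks 20 and 24, but the subjects who can be measured then were selected by the primary outcome. Each was at -100% when closure was confirmed. A between-arm ANOVA on those measurements therefore compares vehicle subjects who closed with CSTC1 subjects who closed. It no longer compares the randomized groups. It can move only if ulcers reopen, and 4:1 allocation leaves few vehicle closers.

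If reopening is similar in both arms, such a test shows about no difference even when CSTC1 closes more ulcers, and that could be misread as loss of effect. If reopening differs, the result tracks reopening and says nothing about closure. Section 2.1.2 says that the study is for registration, so a stray late p-value on a named endpoint is worth preventing.

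**Working it through.** **1. Does the wording reach weeks 20 and 24?** If post-treatment means after the first dose, as in section 10.2.1, these weeks are included. If it means after dosing ends, they are also included. The stopping phrase in section 10.2.1 governs per-protocol membership only; section 2.2.2 has no equivalent.

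**2. Who is due?** Non-closers: last visit at week 16 (sections 4 and 7.6). After week 16, only confirmed closers.

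**3. First possible confirmation.** Section 2.2.1 requires two consecutive visits 2 weeks apart. Visits fall at weeks 1, 2, 3, 4, 6, 8, 10 and 12, so the first literal pair is weeks 4 and 6. Confirmation is possible at weeks 6, 8, 10, 12 and 14 (week 14 by the Summary's week-12 rule).

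**4. Closers' visits on the confirmation clock (+2, +4, +8, +12 weeks; week 12 kept by footnote 11).**

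| Confirmed at week | Follow-up weeks |
|---|---|
| 6 | 8, 10, 14, 18 (and 12) |
| 8 | 10, 12, 16, 20 |
| 10 | 12, 14, 18, 22 |
| 12 | 14, 16, 20, 24 |
| 14 | 16, 18, 22, 26; or 16, 20, 24 under section 4's week-24 rule |

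The last row is a direct contradiction: 14 + 12 = week 26 under section 7.6, but week 24 under section 4.

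Assume that the five confirmation weeks are equally likely. The share of closers due at week 20 is then 2/5 to 3/5, and at week 24 it is 1/5 to 2/5. On fixed weeks it is 5/5 at both.

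**5. Vehicle subjects due.** The plan gives no figure for this. Its sample size is 80 versus 20, with about 125 recruited; 125 split 4:1 is 100 versus 25. Closure rates are not visible, so 30% vehicle closure is assumed, with a range of 20% to 40%. Formula: vehicle n × closure × share due.

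| Vehicle n | Closure | Fixed weeks, week 20 or 24 | Confirmation clock, week 20 | Confirmation clock, week 24 |
|---|---|---|---|---|
| 25 | 30% | 7.5 | 3 to 4.5 | 1.5 to 3 |
| 25 | 20% to 40% | 5 to 10 | 2 to 6 | 1 to 4 |
| 20 | 30% | 6 | 2.4 to 3.6 | 1.2 to 2.4 |

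For example, 25 × 0.30 = 7.5; 7.5 × 2/5 = 3 and 7.5 × 3/5 = 4.5.

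**6. What a late test measures.** All inputs here are assumptions: closure 50% versus 30%, non-closer mean change -40%, reopening 10% in each arm, reopened ulcers averaging -79.5% (midpoint of -99 and -60).
- All subjects at a common visit: 0.5 × (-100) + 0.5 × (-40) = -70, against 0.3 × (-100) + 0.7 × (-40) = -58. The difference is -12 points. With non-closer means of -20 and -60 it is -16 and -8.
- Closers only: 0.9 × (-100) + 0.1 × (-79.5) = -97.95 in both arms. The difference is 0.
- Closers only, reopening 5% versus 20%: -98.98 against -95.90, or -3.1 points. With the rates reversed it is +3.1.

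A 3,000-run simulation used somewhat different inputs: 80:20, closure 50% versus 30%, non-closers around -35% (SD 40), 10% reopening, a two-sample t-test without center, and all closers present late. The all-subject test rejected in 24% of runs (difference -13.3 points). The closers-only test rejected in 5.9% (difference 0.0). With no reopening, the closers-only test cannot be computed because the values do not vary.

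**The case against.** The strongest reply is that the defect is inferred. The ANOVA sentence is one line of a summary and does not say that the test is run at every visit, at weeks 20 and 24, or on measured values only. The same paragraph tests the closure rate at the endpoint although that rate is also defined per visit, so a per-visit definition does not imply a test at each visit. Efficacy conclusions rest on the ITT population, and a closers-only analysis is not an analysis of all ITT subjects. Section 4.1 gives the late visits a durability and safety purpose. The natural place for the tested visits and missing-data handling is section 10.2.2, which is redacted.

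All of this stands and limits the point. A reader might infer that the sponsor will test size change at week 24, or that the plan has no restriction; the documents support neither. What remains is that the visible definition includes weeks 20 and 24, the visible test carries no visit limit, and the attendance rules make a late comparison non-randomized.

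A reader might also infer that early closers miss week 6. That would need confirmation at week 4, but weeks 2 and 4 are not consecutive visits. Nor does a false efficacy signal follow: with equal reopening, the closers-only test rejects at about its nominal rate. The all-subject comparison above illustrates a common visit; it is not power lost at week 24, where non-closers are not measured.

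**Conclusion.** The point holds at low severity. Followed as written, the visible text permits a between-arm ANOVA at weeks 20 and 24 that is conditioned on closure and reflects only reopening, with single-figure expected vehicle numbers under the 30% assumption. Those counts rest on assumed closure rates and evenly spread confirmation times. That only closers are due after week 16 needs no assumption.

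The contradiction between the follow-up clocks is real whatever section 10.2.2 says. A second inconsistency matters for weeks 14 and 16: footnote 4,10, attached to ulcer evaluation, gives non-closers a safety evaluation, while sections 7.5 and 7.6 list ulcer evaluation for them. Week 12 is therefore the last visit clearly due for everyone. The endpoint is secondary, and the primary endpoint and its analysis are not affected.

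**What to change.** 1. In the Protocol Summary and section 2.2.2, and in section 10.2.2 if it does not already say so, limit between-arm tests of size change to visits due for all subjects, with week 12 as the last.
2. Report weeks 20 and 24 by arm as descriptive durability among closers, labelled non-randomized and without a p-value. This still serves the closure-strength question in section 4.1.
3. Reconcile the follow-up timing in sections 4 and 7.6 with the Schedule and section 7.5, including the week-24 versus week-26 end for subjects confirmed at week 14.
4. Before any test later than week 12, reconcile footnote 4,10 with sections 7.5 and 7.6 on whether non-closers have ulcer evaluation at weeks 14 and 16.

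The cost is wording only, with no new data; the downside is that fewer visits carry p-values. If section 10.2.2 already limits the visits, item 1 reduces to aligning the Summary and section 2.2.2 with it; items 3 and 4 remain.

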2.2.3 Safety endpoints

1. Adverse event incidence

2. Change in physical examinations

3. Net change from baseline in laboratory test results (include hemoglobin, hematocrit, RBC, platelet, WBC with differential counts, HbA1c, fasting glucose, AST, ALT, creatinine and BUN)

4. Net change from baseline in vital signs

3. STUDY POPULATION

3.1 Subjects Enrollment

The sample size is determined to be 80 versus 20 subjects (4:1 ratio) for Treatment versus Control groups, 100 subjects in total. To ensure the completion of 100 evaluable (= per-protocol) subjects, around 125 subjects will be recruited. All of the subjects will be recruited in Taiwan. Any subject fulfills all of the recruitment criteria will be screening and/or randomized into the study.

Re-screening for patient's eligibility will be allowed if the patient is willing to participate in the study and one of the following conditions meets:

1. If a patient consents to participate and meets the eligibility criteria but a delay occurs in starting to participate in due to certain change in situation such that some measurement relevant to eligibility became invalid owing to the delay
2. If the cause of screen failure has now resolved or adequately treated such that patient's medications have now stabilized

In these situations, if randomization has not occurred;

1. A new CRF will be used
2. A new Screening number will be assigned to the person
3. The person will be marked as having been re-screened on both the CRF and the site master list
4. The patient needs to sign a new ICF as part of the screening procedure.

It is not appropriate to re-screen a patient if he/she has previously failed to meet the eligibility criteria and no further changes or treatments have been able to indicate that the patient may be suitable.

3.2 Inclusion Criteria

A subject is eligible for the study if all of the following apply:

1. With either gender aged at least 20 years old
2. With at least one diabetic foot ulcer (including ulcers on the lower legs) on the foot and not healing for at least 4 weeks. The largest diabetic foot ulcer will be selected as target ulcer. If two or more ulcers have the largest size, the one with worst grade will be selected. If two or more ulcers have the largest size and grade, the one with longest duration will be selected.
3. The target ulcer is classified as grade 1 to 2 ulcer according to modified Wagner system and with ulcer size of 1cm² to 50 cm²
4. The target ulcer should be confirmed without active infection.
5. Subject should be free of any necrosis or infection in soft and bone tissue;
6. Subject has signed the written informed consent form

